#### **3.2.2 Secondary Efficacy Endpoints and Evaluations**

*Key Secondary Endpoint:*

- For each combination of injected peptide/radioactivity dose range, differences in image quality derived from a  $2 \times 3$  factorial analysis measuring the tumour-to-background ratio in each of the major anatomic sites (descriptive analyses for liver, lymph nodes, bone and lungs)

A qualitative analysis of the image assessed by the independent blinded readers will be performed to back up the quantitative quality measured by tumour-to-background analysis.

*Other Secondary Endpoints:*

- Differences in lesion  $SUV_{max}$  between the two peptide mass dose ranges and the three radioactivity dose ranges measured in the most avid lesions (descriptive analyses for up to a maximum of five lesions per organ in liver, lymph nodes, bone and lungs)
- Differences of absolute number of lesions between the two peptide mass dose ranges and the three radioactivity dose ranges detected in each of the following anatomic sites:
  - Primary site of GEP-NET
  - Lymph nodes
  - Liver
  - Axial/appendicular skeleton
  - Lungs
- The primary and secondary endpoints will also be evaluated on a radioactivity dose/kg of body weight.

*Exploratory Endpoints:*

- Preliminary diagnostic sensitivity of  $^{68}\text{Ga}$ -OPS202 imaging of GEP-NETs by both subject-based and lesion-based analysis compared to standard-of-truth
- Comparison tosstr2 agonist results will be computed for sensitivity analysis
- Differences in  $SUV_{max}$  ratios between the two peptide mass dose ranges and three radioactivity dose ranges for lesions
- SNR calculated from lesion-free volume of interest (VOI) in the liver:  $SUV_{mean}/SUV_{SD}$  between the three radioactivity doses.

### 3.2.3 Safety Endpoints and Evaluations

The safety and tolerability of  $^{68}\text{Ga}$ -OPS202 will be assessed throughout the study by evaluating AEs, clinical laboratory test results (serum chemistry, haematology, and urinalysis), vital signs measurements (blood pressure, heart rate and respiratory rate), electrocardiograms (ECGs), physical examination results and concomitant medication usage.

The following safety endpoints will be evaluated:

- Proportion of subjects experiencing at least one AE of any grade according to National Cancer Institute (NCI) Common Terminology Criteria for Adverse Events (CTCAE version 5.0), including any serious adverse events (SAEs) and suspected unexpected serious adverse reactions (SUSARs)
- Proportion of subjects experiencing at least one AE of grade  $\geq 3$  according to NCI-CTCAE (version 5.0). All AEs will be coded using Medical Dictionary for Regulatory Activities (MedDRA) system organ class (SOC) and preferred term (PT) (as per most recent version)
- Clinically significant changes in physical examination, vital signs, ECG and laboratory findings, which will be recorded by the investigator as AEs.

### 3.2.4 Pharmacokinetic Endpoints

OPS202 plasma concentration will be evaluated at the following timepoints: Baseline pre-dose (T0), 5 min, 15 to 45 min, 1h, 2h, 3h and 6h after the Ga-OPS202 i.v. administration at the corresponding visits (Visit 2 and Visit 3). Urine collection to determine renal excretion of OPS202 will be performed over the first 6 hours in two separate samples: 0h to 3h and 3h to 6h after the Ga-OPS202 i.v. administration at the corresponding visits (Visit 2 and Visit 3).

OPS202 PK parameters include the following:

- Maximum plasma concentration ( $C_{max}$ )
- Area under the plasma concentration time curve from time 0 to the time of the last quantifiable concentration ( $AUC_{last}$ )
- Area under the plasma concentration time curve extrapolated to infinity ( $AUC_{0-\infty}$ )
- Elimination half-life ( $T_{1/2}$ )
- Total plasma clearance (CL)
- Volume of distribution (V)
- Excreted amount of OPS202 in the urine over each time interval (see Section 3.2.4) as well as the 6-hour cumulative amount of unchanged OPS202 excreted into the urine ( $A_e$ ).

### 3.3 Randomisation and Blinding

This is an open-label study and there is no blinding for the administration of the IIP nor for its doses (peptide mass dose as well as radioactivity dose).

An independent statistician (the sponsor's randomisation manager) will prepare the master list of randomisation numbers for this study. This list will be produced in blocks, on a balance ratio for the three sequences summarized in Table 4.

**Table 4 Sequences of Peptide Mass Doses and Radioactivity Doses**

	Visit 2 (D1)	Visit 3 (between D16-D22)
Sequence A	5-20µg / 40-80 MBq	30-45µg / 100-140 MBq
Sequence B	5-20µg / 100-140 MBq	30-45µg / 160-200 MBq
Sequence C	5-20µg / 160-200 MBq	30-45µg / 40-80 MBq

After eligibility is confirmed at Visit 2 (Day 1), subjects will be assigned to a randomisation number and to the associated sequence of study arm, in sequential order within each centre.

Each subject will receive, at Visit 2 and Visit 3, the peptide mass dose and radioactivity dose associated to this randomisation number. The randomisation number and the dose ranges will be provided by the electronic case report form (eCRF), which will assign the subjects in a study arm according to the predefined randomisation list. The investigator will under no circumstances be able to change the randomisation number and the sequence of treatment arms allocated to the subject.

Recruitment will stop once 24 evaluable subjects have been randomised and completed the study procedures. Each non-evaluable subject (see Section 3.6) will be replaced by a subject who will receive the same dose ranges sequence as the one assigned to the replaced subject. In this context, a mirror randomisation list will also be produced to randomise the replacement subjects. In this mirror randomisation list, only the replacement randomisation numbers of non-evaluable subjects will be considered.

The randomisation list will be produced for 24 randomisation numbers (from CCI ) and for 24 replacement randomisation numbers (from CCI ). For instance, the possible replacement randomisation number CCI will have to be used to randomise the possible replacement of subject who was randomised with randomisation number CCI

Randomised subjects who terminate their study participation for any reason before administration of the first dose of randomised study drug will retain their randomisation numbers (i.e. these numbers will not be reused). The next subject will be given another randomisation number, even if he/she should receive the same sequence of study arms.

Subjects who complete Visit 2 and do not complete the imaging of Visit 3 will be replaced. Also, if the images at Visit 2 or at Visit 3 are of unacceptable radiological quality (see Section 3.6), the subject will be replaced. Quality will be assessed by the imaging core lab (ICL) within 5 days of submission.

To limit the extension of study duration if the last two potentially evaluable subjects (randomisation numbers CCI ) should be non-evaluable, corresponding replacement subjects (randomisation number CCI , respectively) will be recruited as soon as possible. If both potentially evaluable and replacement subjects are evaluable at the end of the study, the subjects assigned to randomisation numbers CCI will be included in the efficacy and safety analysis whereas the replacement subjects assigned to randomisation numbers CCI will be included only in the safety analysis. Therefore, a total of at least 25 subjects will be enrolled in the study to ensure the 48 PET scans for the analysis.

The sponsor's randomisation manager will keep the master randomisation lists. The master lists and the copy supplied to the contract research organisation (CRO) in charge of the eCRF and the ICL in charge of blinding of the imaging scans will be kept confidential in a secure location. Access to these randomisation lists must be restricted until authorisation is given to release them for final analysis.

### 3.4 Study Imaging Product and Dosage

The IIP is provided as a sterile two-vial radiolabelling kit constituted of freeze-dried powder containing 50 mg non-radiolabelled precursor OPS202 and excipients (Vial A) and the solvent for reconstitution (Vial B) to be used prior to radiolabelling.

The final radiolabelled IIP ( $^{68}\text{Ga}$ -OPS202) (one batch per kit and per subject dose) will be prepared in the local radiopharmacy at the clinical trial sites in a two-step aseptic compounding process:

- Reconstitution of the sterile vial A containing the OPS202 precursor and excipients with 1 mL of the solvent for reconstitution consisting of a solution of sterile sodium acetate from Vial B,
- Radiolabelling of the precursor OPS202 achieved by the addition of a 5 mL sterile hydrochloric acid solution of  $^{68}\text{Ga}$ , eluted from a sterile pharmaceutical grade  $^{68}\text{Ge}/^{68}\text{Ga}$  generator.

The test product,  $^{68}\text{Ga}$ -OPS202, will be administered i.v. over one minute, at one of the doses shown in Table 3, and according to the randomisation of the subject.

A more detailed description of administration procedures is given in Section 6.1.1.

The investigators will receive a certificate of conformity and a certificate of analysis for each IIP batch. A Material Safety Data Sheet is also available.

The IIP packs and all vials will be labelled. Each label will be designed in accordance with Appendix 13 of the European Union Good Manufacturing Practices (EU-GMP) (see [Appendix 1](#)) and in accordance with specific local requirements if any. After reconstitution and radiolabelling the vial will be included in a lead container. This lead container will be labelled according to Appendix 13 of EU GMPs (see [Appendix 1](#)) and according to specific local requirements if any.

Final IIP reconstitution, radiolabelling, quality control (QC) and IIP release will be performed at the study site's radiopharmacy facility. Labels for the final IIP and containers can be provided by the sponsor if required by the clinical site.

The IIP (OPS202, cold precursor) will be packaged and delivered to the investigational sites/central or interim storage facilities. A sufficient quantity of IIP will be supplied as well as an acknowledgement of receipt form. No code break envelopes will be supplied as the double blinding relates to the independent central readers.

The investigator, or designee, will only administer IIPs to subjects included in this study. Each subject will only be given the IIP carrying his/her number. The dispensing by the responsible pharmacist and the administration to each subject will be documented in the eCRF.

The peptide mass dose ranges and the radioactivity dose ranges are summarized in [Table 3](#), and their sequence of administration in [Figure 1](#).

### 3.5 Study Duration

This study will consist of up to a 2-week screening period, an approximately 3-week imaging period, and a 2-week follow-up period. Subjects are expected to participate in this study for a minimum of 6 weeks and up to 7 weeks.

The subject's participation in the study will be considered to have ended at the time of the last visit (Visit 4 or End of Study/Early Withdrawal Visit), which should occur approximately 2 weeks after their last IIP administration.

### 3.6 Stopping Rules and Discontinuation Criteria

There are no formal rules for early termination of this study. During the conduct of the study, SAEs will be reviewed (see [Section 8.1.3](#)) as they are reported from the study centres to identify safety concerns. The study may be terminated by the sponsor at any time.

A subject may discontinue participation in the study at any time for any reason (e.g., withdrawal of consent, AE). The investigator and/or sponsor can withdraw a subject from the study at any time for any reason (e.g., protocol deviation as defined in [Section 12.1.2](#), noncompliance with the protocol conditions or AE).

If a subject's Visit 2 Ga-OPS202 PET/CT scan images are non-evaluable for whatever reason, the subject will be discontinued from the study. This study has a small number of subjects requiring two timepoints for image evaluation.

Each non-evaluable subject will be replaced by a subject who will receive the same IIP sequence as the one assigned to the replaced subject (see [Section 3.3](#)). A non-evaluable subject is one for whom any of the following image sets are missing or of unacceptable quality for ICL:

- 1) Visit 2 and/or Visit 3 Ga-OPS202 PET/CT scans, as these provide the "standard-of-truth" information and both are needed for the factorial design
- 2) Previous somatostatin receptor scans, which confirm the presence of sstr2 in the tumour

- 3) All images will be reviewed and assessed by ICL to ensure there are no quality issues relating to artefacts that are detrimental to the study endpoints. These primarily consist of the following:
- (a) Metal implants
  - (b) Patient motion
  - (c) Excessive breathing artefacts between the PET and CT scan images.

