**Combinations of Studied Peptide Mass Dose Ranges and Radioactivity Dose Ranges**

Peptide mass dose range	Radioactivity dose range		
	40-80 MBq	100-140 MBq	160-200 MBq
5 – 20 µg	8 scans	8 scans	8 scans
30 – 45 µg	8 scans	8 scans	8 scans

Each of the 24 evaluable subjects will receive two different peptide/radioactivity ranges combinations.

Hence, 48 PET/CT scans will be analysed (8 in each combination peptide/radioactivity dose range)

The lowest peptide mass dose range with the highest radioactivity dose range can only be obtained with a new Ge/Ga-generator. It is anticipated that the 40 to 80 MBq radioactivity dose range will provide a poor diagnostic signal, particularly for subjects with a high body mass index (BMI). However, with the “as low as reasonably achievable” (ALARA) principle, this will be studied as well as the higher peptide mass dose.

Ga-OPS202 consists of 50 µg of peptide in a total volume of 6 mL (8.33 µg/mL). Sampling of 0.5 mL for quality control yields 5.5 mL solution from which the volume to be injected into the subject is withdrawn. This volume is calculated to obtain the target peptide mass dose and the desired radioactivity dose, taking into account the elapsed time between the syringe preparation and the intravenous (i.v.) administration of Ga-OPS202 (decay of Ga).

[figure not shown]
Subjects will be assigned to one of three study arms (see figure). At the end of the study, each subject will provide two sets of images corresponding to two combinations of peptide / radioactivity dose ranges. The sets of images for the primary endpoint, and most of the secondary endpoints will be sent to an imaging core lab (ICL) for central blinded reading by two independent experienced radiologists and a third for adjudication of discordances. The readers will be specifically trained for this protocol.

All decisions regarding subjects’ medical management will be made locally by the treating physicians (images read locally for this purpose). The ICL/central readers will only evaluate the study endpoints and will not make any decisions regarding subject management.

*Duration of participation for a subject*

Subject participation in the study is estimated to last approximately 7 weeks and will include:

- Visit 1: A screening period up to 2 weeks

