##### *Sample size and power considerations:*

It is anticipated that a total of 24 evaluable subjects will complete the study (i.e., receive two of the six combinations of dose ranges offered per protocol) and therefore to account for illegible or missing scans subjects with unacceptable scan images will be replaced in order to obtain at least 8 evaluable subjects in each study arm. To limit the extension of study duration if the last two potentially evaluable subjects (CCI [REDACTED]) should be non-evaluable, corresponding replacement subjects (randomisation number CCI [REDACTED], respectively) will be recruited as soon as possible. Therefore, a total of at least 25 subjects will be enrolled in the study to ensure the 48 PET scans for the analysis.

This is considered appropriate for a descriptive analysis and it is not based on formal statistical sample size calculation. In the event that a subject misses an imaging exam and/or measurement relevant to the primary and key secondary endpoints, an additional subject will be recruited as a replacement to ensure an adequate sample size in the "per protocol set" for evaluation of overall lesions.

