2.1.2 Per Protocol population (PP)

The Per Protocol (PP) population includes all randomised subjects for whom no major protocol violations/deviations impacting primary endpoint results occurred.

Any subject having a PET/CT scan which is non-evaluable/non-readable or having not meet the required minimum number of lesions by ICL readers and/or adjudicator will be considered impacting primary endpoint results, and therefore will be excluded from PP population. If there are disagreements between the readers, the adjudicator will have the final verdict if scans are evaluable or readable and how many number of lesions are seen.

Criteria for exclusion from the PP population will be provided in a separate Protocol Deviations Document (PDD) and Protocol Deviations Specifications.

Of note, if the screening visit duration is extended due to confirmation by ICL of eligibility regarding somatostatin receptor scan, this will not be considered a protocol deviation.

The Per Protocol criteria should be produced in advance of the database lock and generation of the PP population, and should be done using the first 50% of the subjects to avoid potential bias. In addition, a more extensive list of protocol deviations may be defined and reported in data listings.

Data will be excluded from the PP population on a subject basis and not on a visit basis. Of note, in case a subject performs only one of the two planned injections, he will be excluded from the PP population.

Reasons for subject exclusion from PP population will be presented in a summary table by dosing arm / sequence.

As specified in the study protocol section 3.3, replacement subjects of subjects CCI [REDACTED] will be recruited as soon as possible. In case subjects CCI [REDACTED] are found to be evaluable, corresponding replacement subjects will be excluded from PP population, regardless of the presence of major of protocol deviations (and provided CCI [REDACTED] have actually been replaced). Of note, correspondence between replacement subjects and their original subject will be obtained using the listing of randomised subjects from Medidata Balance (eCRF module for randomisation). This listing will be imported at the time of programming the statistical analysis.

As a results, PP population is expected to include 24 subjects: 8 subjects in each of the three study arms, who did not present with any major protocol deviation impacting PP and who were not replaced for any reason.

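### Scans that fail through low activity would be replaced and excluded rather than counted, which can flatter the 40-80 MBq cells; failures should be coded by cause, tabulated by dose cell and scored in a sensitivity analysis

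*Protocol*

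**What the plan says.** **Who is non-evaluable.** Protocol 3.6 defines a non-evaluable subject as one for whom "any of the following image sets are missing or of unacceptable quality for ICL". The first item listed is the Visit 2 and/or Visit 3 PET/CT, with no limit on cause. The third item describes an imaging core lab (ICL) review "to ensure there are no quality issues relating to artefacts that are detrimental to the study endpoints" and names metal implants, motion and breathing as the primary examples.

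**What follows.** For Visit 2, Protocol 3.6 states that if the "scan images are non-evaluable for whatever reason, the subject will be discontinued from the study". Protocol 3.3 adds that "if the images at Visit 2 or at Visit 3 are of unacceptable radiological quality (see Section 3.6), the subject will be replaced". On the replacement, Protocol 3.6 says: "Each non-evaluable subject will be replaced by a subject who will receive the same IIP sequence as the one assigned to the replaced subject". The Synopsis sample-size text gives the purpose: "to account for illegible or missing scans subjects with unacceptable scan images will be replaced".

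**Analysis.** SAP 2.1.2 excludes from PP "Any subject having a PET/CT scan which is non-evaluable/non-readable", and it does so by subject, not by visit. (It also excludes on a minimum lesion number, which is a separate matter.) PP is the primary population (SAP 2.4). Missing efficacy data are not imputed (SAP 3.2.3.1). The optimal range is selected on the highest relative lesion count observed (SAP 3.2.1.1).

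**Expected image quality.** The Synopsis anticipates that the "40 to 80 MBq radioactivity dose range will provide a poor diagnostic signal, particularly for subjects with a high body mass index". Protocol 1.5 is milder: it expects the low range to be near or below optimal in some subjects.

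**The concern.** In a study meant to find the optimal radioactivity range, a scan that cannot be read because too little activity was given for that body size is a result of the dose. The plan treats it like a scan spoiled by movement: the subject leaves PP and the place is refilled in the same sequence until eight evaluable subjects are reached. The 40-80 MBq cells would then hold only scans that worked.

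The effect would not stay in those cells. Arm A gives 40-80 MBq at Visit 2, Arm C gives it at Visit 3, and Arm B never gives it. Because exclusion is by subject, the paired cells of Arms A and C (30-45 µg/100-140 MBq and 5-20 µg/160-200 MBq) would also lose their hard-to-image subjects, while both Arm B cells would keep theirs. The two peptide comparisons within the higher activity ranges would each set a selected cell against an unselected one, in opposite directions. The Synopsis plans to examine the peptide-by-radioactivity interaction, which is where this pattern would appear.

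The other planned analyses do not recover the failures. All secondary and exploratory analyses are on PP only (SAP 3.2.1.2), including the MBq/kg analysis, whose ranges are set from the PP distribution. The randomised-population analysis is optional and post hoc, and an unreadable scan brings no lesion count to it.

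**Working it through.** **The plan's own figures.** 3 arms × 8 = 24 subjects; × 2 visits = 48 scans; 48/6 = 8 per cell; 48/3 = 16 per activity range. Adding one or two early replacements to 24 gives 25 or 26, consistent with the stated minimum of 25. There is no power calculation to reproduce, because the study is descriptive.

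**Effect on the 40-80 MBq mean.** Let *m* be the mean relative lesion count among readable 40-80 MBq scans and *f* the share of 40-80 MBq scans that fail through low signal. Neither is in the documents; both are assumed. The plan reports *m*. Scoring a failed scan as no lesions detected gives *m*(1 − *f*), an overstatement of *mf*. Filling 16 low-activity places removes an expected 16*f*/(1 − *f*) failed scans. The chance of at least one failure among the first 16 is 1 − (1 − *f*)^16. With *m* = 0.80:

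| *f* | Mean with failures as 0 | Overstatement | Expected failed scans removed | Chance of at least one in first 16 |
|---|---|---|---|---|
| 0% | 0.80 | 0 | 0 | 0 |
| 5% | 0.76 | 0.04 | 0.8 | 56% |
| 10% | 0.72 | 0.08 | 1.8 | 81% |
| 20% | 0.64 | 0.16 | 4.0 | 97% |

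For *m* between 0.6 and 1.0, the overstatement is 0.03-0.05 at 5%, 0.06-0.10 at 10% and 0.12-0.20 at 20%. In every row the primary table still shows 8 evaluable scans per cell. Zero is the lowest score a failed scan can take, so *mf* is the largest overstatement for a given *f*.

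**Effect on the paired cells.** Assume 20% of patients are hard to image, average 0.60 rather than 0.80 at the higher activities, and all drop out of Arms A and C. An unselected Arm B cell then averages 0.8 × 0.80 + 0.2 × 0.60 = 0.76, against 0.80 in a selected cell. The 30-45 µg minus 5-20 µg difference is:

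- at 100-140 MBq (Arm A minus Arm B): 0.80 − 0.76 = +0.04;
- at 160-200 MBq (Arm B minus Arm C): 0.76 − 0.80 = −0.04.

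For scale, with an assumed SD of 0.20 and 8 scans per cell, the standard error of a difference between two cells from different arms is 0.20 × √(2/8) = 0.10.

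**The case against.** **The mechanism is inferred.** The protocol expects poor or below-optimal images at 40-80 MBq; it never says they will be unreadable. The quality problems it names are mainly artefacts unrelated to dose, weight is capped at 110 kg, and the core-lab quality methods are left to the Imaging Review Charter, which is not among the documents. A noisy but readable scan stays in PP and contributes its lower lesion count, quality score and signal-to-noise ratio. This stands, and it limits confidence. It does not remove the point: the first item in Protocol 3.6 and the reader route in SAP 2.1.2 are not limited to artefacts, and low-signal scans are not exempted.

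**A reader might infer that the losses would be invisible.** The documents do not support that. Reasons for PP exclusion are tabulated by arm (SAP 2.1.2 and 3.2.4; Protocol 10.4.3), withdrawal reasons likewise (SAP 3.2.5), and replacement subjects stay in the randomised population (SAP 2.1.1). An excess of exclusions in Arms A and C over Arm B would show. What is missing is any table by dose cell and any requirement to separate low signal from artefact.

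**A reader might infer that a spurious interaction is to be expected.** The ±0.04 rests on stacked assumptions and is less than half the illustrative standard error of 0.10. It shows the direction the selection would take, not a predicted result.

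**A reader might want the replacement and discontinuation rules rewritten so that the other scan of the pair is always kept.** In Arm A that scan does not exist, because a subject whose Visit 2 scan fails is discontinued before Visit 3. Changing the rule would mean further injections and scans, and the bias can be made visible without it. In Arm C the Visit 2 scan has been acquired, and the optional randomised-population analysis could bring it back if it were run.

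**Conclusion.** The point holds as a gap in the plan, not as a demonstrated bias. Non-evaluable scans are replaced and excluded without regard to cause, in a population on which the activity range is selected and at a dose for which the protocol itself expects poor signal. If any 40-80 MBq scans fail through low activity, the reported low-activity means are too high, and the paired cells of Arms A and C are selected while Arm B is not. If none fail that way, the bias is zero.

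The size cannot be known from the documents. The 0.80 to 0.64 range depends on an assumed readable-scan mean of 0.80, assumed failure rates of 0% to 20%, and scoring every failure as zero. As written, the outputs would not show how many scans in each dose cell failed through low signal. This should be fixed; confidence is moderate.

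**What to change.** Leave the dosing, discontinuation and replacement rules as they are, and change what is recorded and analysed.

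1. **Cause code.** Each scan judged non-evaluable by the ICL or the readers is coded as technical (missing, motion, implant, misregistration, extravasation) or insufficient signal. The person coding must be blind to dose. Protocol 3.8 describes blinding for the readers but does not expressly cover the quality check, and under Protocol 3.3 the ICL is supplied with the randomisation list.
2. **Failure table (SAP 3.2.1.1).** For each of the six cells, over all injected subjects including those replaced, show scans acquired and scans non-evaluable by cause, beside the relative lesion count.
3. **Sensitivity analysis (SAP 3.2.1.1 and 2.4).** In place of the optional post-hoc randomised-population analysis, pre-specify a repeat of the primary table over all acquired scans. Score insufficient-signal scans as zero lesions detected, so the ratio is 0 whenever the available CT shows at least one lesion. The standard-of-truth normally combines both visits, so use the single-visit CT for subjects discontinued after Visit 2. Include the other scan of the pair where it was acquired.

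**Cost.** One reason code on the quality form, short SAP wording and one or two extra tables. The low-activity means may look less favourable. No extra subjects, readers or procedures are needed.
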